8.2.1 Number of patients to be studied

Planned number of patients to be included in the entire study is 400. These will be distributed as follows:

• Pilot Study

o 100 patients: 50 patients prescribed Saxenda[®] and 50 patients prescribed Victoza[®]

• Full study

o 300 patients: 150 patients prescribed Saxenda® and 150 patients prescribed Victoza®

Anticipated number of patients to be included in each of the two selected EU countries:

- Pilot study: 25 patients prescribed Saxenda[®] and 25 patients prescribed Victoza[®]
- Full study: 75 patients prescribed Saxenda® and 75 patients prescribed Victoza®

8.2.2 Inclusion criteria

To be eligible for the study, patients will be required to meet both of the following inclusion criteria:

1. Initiation of Saxenda® or Victoza® (initiation is defined as no prescription of the same brand within the previous 12 months).

Protocol		Date:	23 November 2015	Novo Nordisk
Study ID: NN8022-4241		Version:	5.0	
UTN: U1111-1185-3661		Status:	Final	
EU PAS No.:	CONFIDENTIAL	Page:	22 of 53	

2. Informed consent obtained before any study-related activities. Study-related activities (e.g. data collection) are any procedures that are carried out as part of the study, including activities to determine suitability of the study.

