been shown to reduce hyperglycaemia in patients with type 2 diabetes mellitus (T2DM). The mechanisms of action for liraglutide include stimulation of insulin secretion and decrease of glucagon secretion, both in a physiological and glucose dependent-manner. The effects of liraglutide also include reduced sensation of hunger and increased satiety, leading to decreased food intake and subsequent weight loss.

Victoza[®] is indicated for the treatment of adults with T2DM at doses of 1.2 mg and 1.8 mg, and received marketing authorisation from the European Medicines Agency (EMA) in June 2009. Saxenda[®] (liraglutide 3.0 mg) is indicated as an adjunct to a reduced-calorie diet and increased physical activity for weight management in adults who are obese, or adults who are overweight with at least one weight-related comorbidity. The efficacy of Saxenda[®] was demonstrated in five phase 2 and 3 clinical trials involving around 5,800 obese/overweight patients, which showed that more patients administered Saxenda[®] achieved clinically relevant weight loss than those treated with placebo. Saxenda[®] received marketing authorisation from the EMA in March 2015.

As defined in the Risk Management Plan (RMP) for Saxenda[®], a retrospective drug utilisation study (DUS) to investigate patterns of use of Saxenda[®] and Victoza[®] in routine clinical practice has been requested by the EMA as a post marketing requirement. As is the case with any medicinal product, real-world use of Saxenda[®] or Victoza[®] may differ from the approved indication or recommendations outlined in the Summary of Product Characteristics (SmPC) (1, 2). Considering that these two liraglutide products with the same strength and formulation will be available for different indications with different doses, there is the potential for inadvertent use of one or the other product for either indication. The DUS will allow assessment of usage patterns of liraglutide for weight management, and thereby could refine pharmacovigilance planning and risk management.

7 Research question and objectives

The aim of this study is to investigate in-market utilisation of liraglutide for weight management. Specifically, the primary and secondary objectives are the following:

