8.1 Study design

8.1.1 Type of study

This DUS is a non-interventional, multi-centre Post Authorisation Safety Study (PASS) to investigate the use of Saxenda[®] and Victoza[®] in clinical practice in patients who have initiated treatment in the Saxenda[®] postmarketing period. The DUS involves retrospective review of patients' medical records in two selected European Union (EU) countries 24 months after launch of Saxenda[®] in each of the countries. Physician sampling will be built using several tools, including intelligence databases, e.g., IMS LifeLinkTM, in order to obtain a representative sample of Saxenda[®]/Victoza[®] prescriptions according to physician specialty and geography. This data source will be complementary to the full study and will be obtained on a quarterly basis, during the study period. It will provide, on a national level for the two targeted countries, the distribution of sites and prescribers' specialty. It will not identify individual prescribers, but rather guide the site selection for the study performed by Therefore, IMS LifeLinkTM will be used a priori to refine the sampling strategy (using regional and specialty distribution of prescribers), and a posteriori to assess the representativeness of prescribers and patients, for both the pilot and full study.

A case report form (CRF), including all the desired data elements, will be available to the selected sites; one CRF is to be completed per patient prescribed Saxenda® or Victoza®. The CRF may be completed by a trained healthcare professional at the site, or by a trained external medical record abstractor. The data will be entered pseudonymised into the CRFs.

A pilot study, to be embedded in the full study, will be conducted 6 months after launch of Saxenda[®] in each of the two countries, i.e., prior to the full DUS. The objective of the pilot study is to evaluate the feasibility of the full DUS. The feasibility will be evaluated on three main parameters:

- 1. Possibility of identifying physicians prescribing Saxenda®/Victoza® and participating sites
- 2. Possibility of identifying patients treated with Saxenda® or Victoza®

Protocol		Date:	23 November 2015	Novo Nordisk
Study ID: NN8022-4241		Version:	5.0	
UTN: U1111-1185-3661		Status:	Final	
EU PAS No.:	CONFIDENTIAL	Page:	19 of 53	

3. Availability and quality of the variables used to determine the specified endpoints (see section 7.3)

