8.2 Setting

Since the purpose of this study is to investigate real-world, in-market utilisation of liraglutide, patients will be identified based on the prescription rather than on a specific diagnosis. The study will target first-time patients of Saxenda® or Victoza® by identifying a representative sample of physicians who treat diabetic or obese patients for whom Saxenda® or Victoza® can be prescribed. These include general practitioners (GPs), endocrinologists and cardiologists (or other diabetes and obesity specialists) from a variety of settings (e.g., office-based vs. hospital-based, urban vs. rural). Once prescribers of Saxenda® or Victoza® are identified, these will be oversampled to ensure adequate numbers of prescribers (and therefore patients).

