8.2.3 Exclusion criteria

- 1. Patients or physicians who previously participated in interventional programs for Saxenda[®] or Victoza[®] will not be eligible to participate in the study.
- 2. For the full study, sites and patients included in the pilot will be excluded.

8.2.4 Withdrawal criteria:

The patient may withdraw at will at any time.

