8.2.6 Flowchart

The data collection period for Saxenda[®]/Victoza[®] will be the interval between the launch date of Saxenda[®] to the index date of the pilot or full study, respectively. Table 1 and Table 2 show the data to be collected respectively for Saxenda[®] and Victoza[®] patients at different time points in relation to initiation of treatment. Data collection will encompass the following treatment periods for Saxenda[®]: (1) a time frame of 6 months prior to treatment initiation, (2) treatment initiation, (3) 4-12 weeks post treatment initiation, (4) 16-24 weeks post treatment initiation, and also (5) throughout the entire treatment period. Data collection will encompass the following treatment periods for Victoza[®]: (1) treatment initiation, and (2) throughout the entire treatment period.

Protocol	UTN: U1111-1185-3661	Date:	23 November 2015	Status:	Final	Novo Nordisk
Study ID: NN8022-4241	EU PAS No.:	Version:	5.0	Page:	23 of 53	

Table 1 - Saxenda® patients¹

Weeks in relation to initiation of treatment/time of first prescription	Prior to treatment initiation	0	4 – 12 weeks	16 – 24 weeks	Throughout the treatment period ²
Visit window			+4 weeks	+4 weeks	
Demography ³		X			
Co-morbidities ⁴	X				
Body Weight		X^5		X^6	
Adult height	X				
BMI		X^5			
Brand name		X			
Indication prescribed		X			
Target dose prescribed		X			
Current dose ⁷			X	X	
Treatment start date		X			
Treatment stop date					X
Concomitant medication with GLP-1					
receptor agonists					X
(Brand name and start date)					

- 1) Inclusion criteria must be fulfilled (incl. obtained informed consent) before data extraction is performed
- 2) Censoring at 24 months after launch
- 3) Sex, age
- 4) Diagnosis of or treatment of pre-diabetes, type 2 diabetes mellitus (T2DM), hypertension, dyslipidaemia and/or obstructive sleep apnoea.
- 5) Latest recording within 6 months before first prescription of Saxenda®
- 6) If not available the earliest subsequent body weight and date of measurement should be recorded
- 7) If treatment discontinuation occurs prior to/between the specified time points, the dose of Saxenda® at time of treatment discontinuation should be recorded.

Protocol		Date:	23 November 2015	Novo Nordisk
Study ID: NN8022-4241		Version:	5.0	
UTN: U1111-1185-3661		Status:	Final	
EU PAS No.:	CONFIDENTIAL	Page:	24 of 53	

Table 2 - Victoza® patients¹

Weeks in relation to initiation of treatment/time of first prescription	0	Throughout the treatment period ²

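### Initiation is defined by brand and prior liraglutide use is not collected, so the primary Saxenda BMI and 5% weight-loss endpoints mix two kinds of baseline that cannot be separated later

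*Protocol*

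**What the plan says.** - **Entry.** Sections 3.5 and 8.2.2 define a new starter by brand: "initiation is defined as no prescription of the same brand within the previous 12 months". Section 8.2 states: "The study will target first-time patients of Saxenda® or Victoza". The exclusions in 8.2.3 cover earlier participation in interventional programmes and, in its second criterion, "For the full study, sites and patients included in the pilot will be excluded". Neither removes prior use of the other liraglutide brand.
- **Baseline.** Table 1, footnote 5 (Section 8.2.6) takes weight and BMI as "Latest recording within 6 months before first prescription of Saxenda". No earlier weight is collected.
- **GLP-1 receptor agonists.** Table 1 and Sections 7.3 and 8.3 record these for Saxenda patients only as concomitant medication during Saxenda treatment (brand and start date). Use before Saxenda is not in the variable lists of 3.6 and 8.3, and 8.4 names 8.3 as the list of data to be collected.
- **Endpoints.** The BMI bands and the 5% weight-loss counts at 16–24 weeks are primary (7.3). Both feed the outside-label proportion that 8.7.2 calls the main analysis.
- **Reason for the study.** Section 6 foresees crossover between the products: "there is the potential for inadvertent use of one or the other product for either indication".

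**The concern.** Both products contain liraglutide, so the brand rule treats a direct switcher as a new starter although part of any weight change may already have occurred. Section 7.1 refers to initial BMI and initial body weight but does not say what initial means for a patient already on liraglutide. The primary endpoints therefore pool patients whose reference weight precedes any liraglutide with patients whose reference weight may not.

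An analysis plan cannot repair this, because it cannot stratify on something never abstracted from the chart. A reader of the final report who sees patients continuing Saxenda with less than 5% loss could not tell how many had already lost weight on Victoza. Section 8.9 discusses exposure misclassification and incomplete records but not switching.

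**Working it through.** **1. The plan's own figures.** The protocol gives patient numbers only: 2 × (25 + 25) + 2 × (75 + 75) = 100 + 300 = 400, as stated in 8.2.1. The full study has 2 × 75 = 150 Saxenda patients. No figure for switching or precision is given, so everything below that needs a switcher share or a prior loss is an assumption.

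**2. Threshold arithmetic.** Let L be the fraction of weight lost on Victoza before the Saxenda baseline was measured.

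- Pre-liraglutide BMI recorded below 30: from 30 up to 30/(1 − L).
- Pre-liraglutide BMI recorded below 27: from 27 up to 27/(1 − L).
- Total loss needed to score 5% on Saxenda: 1 − 0.95 × (1 − L).

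| L (assumed) | Recorded <30 | Recorded <27 | Total loss needed |
|---|---|---|---|
| 3% | 30.0–30.9 | 27.0–27.8 | 7.85% |
| 5% | 30.0–31.6 | 27.0–28.4 | 9.75% |
| 7% | 30.0–32.3 | 27.0–29.0 | 11.65% |

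Example: a BMI of 31.0 with a 5% prior loss is recorded as 31.0 × 0.95 = 29.45. A further 3% loss on Saxenda scores as 3%, while the loss since starting liraglutide is 1 − 0.95 × 0.97 = 7.85%.

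**3. How many would change 5% status.** By simulation (400,000 draws per scenario), total loss from the pre-liraglutide weight was taken as normal, with a share f of it occurring before the switch. The table counts switchers with at least 5% total loss but less than 5% from the Saxenda baseline. A 10% switcher share is 15 of 150 patients; 20% is 30.

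| Total loss, mean (SD) | f | Switchers changing status | Patients, 10% share | Patients, 20% share |
|---|---|---|---|---|
| 6% (5) | 0.3 | 15.9% | 2.4 | 4.8 |
| 6% (5) | 0.5 | 34.1% | 5.1 | 10.2 |
| 6% (5) | 0.7 | 54.3% | 8.1 | 16.3 |
| 8% (6) | 0.3 | 12.4% | 1.9 | 3.7 |
| 8% (6) | 0.5 | 29.3% | 4.4 | 8.8 |
| 8% (6) | 0.7 | 56.8% | 8.5 | 17.0 |

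The range is about 2–9 patients (1–6 percentage points) at a 10% share and 4–17 patients (2–11 points) at 20%. It assumes that all 150 have both weights and are still on treatment; with fewer such patients the counts fall.

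For scale, the 95% half-width 1.96 × √(p(1 − p)/150) is 4.8 points at p = 10% and 8.0 points at p = 50%.

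**4. BMI bands.** Assume pre-liraglutide BMI is normal with mean 33 or 35 and SD 5, cut off below 27, and L is 3–7%. At a 20% switcher share, about 2–6 of 150 patients cross 30 and about 1–3 cross 27.

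Not every crossing changes label status. Type 2 diabetes is a qualifying comorbidity (7.3), so a switcher who has it stays on-label between 27 and 30. There is also an opposite route: 8.3 lets glucose-lowering therapy under ATC code A10 stand as evidence of dysglycaemia, and the PASS information table codes liraglutide as A10BX07. Earlier Victoza, even if given for weight, could be read as a comorbidity and move a patient on-label.

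**The case against.** Including switchers is defensible. Section 8.2.5 wants as broad a population as possible, and switchers are genuine Saxenda users. That stands, and it is why the remedy does not exclude them. Several stronger readings are tempting, and the documents do not support them:

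- **That 8.2 and 8.2.2 contradict each other.** First-time use in 8.2 can be read per brand, which agrees with the inclusion rule. The baseline issue remains on either reading.
- **That the endpoints misclassify switchers.** This assumes initial means before any liraglutide, and the protocol does not say so. A patient with BMI 29.4 and no comorbidity at the first Saxenda prescription may be correctly scored outside label. What can be said is that two baselines are mixed.
- **That outside-label use is overstated.** The BMI effect has no uniform direction, for the reasons in step 4 of the working.
- **That every switcher has an on-drug baseline and none can be seen.** A patient who stopped Victoza months earlier, or was weighed before starting it, may have an off-drug value. Victoza overlapping Saxenda would appear as concomitant use. Only clean switches are invisible.
- **That Victoza use for weight management is undercounted.** Use before Saxenda's launch lies outside the collection period. A post-launch Victoza starter who later moves to Saxenda fits both groups, while 8.1.1 says "one CRF is to be completed per patient prescribed" either product, with no assignment rule. But the Victoza group has a fixed size, so such a patient leaves both numerator and denominator, and the size of any effect cannot be derived.

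It is also fair that the count of switchers is not the count of changed classifications, and that at the low end of the scenarios the effect is smaller than sampling error.

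**Conclusion.** The concern holds in a limited form. The brand-based entry rule, together with the absence of any prior liraglutide or GLP-1 variable, means that the primary BMI and 5% weight-loss endpoints, and the outside-label proportion built on them, mix two kinds of baseline. Clean switchers cannot be separated afterwards.

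The 5% counts are the most exposed. For any patient who lost weight on Victoza, the loss scored on Saxenda is smaller than the total. Roughly 2–17 of 150 patients would change status at assumed switcher shares of 10–20%, which at the upper end is as large as the sampling error or larger. The threshold arithmetic is exact for a given prior loss; the patient counts rest wholly on the assumed shares and weight-loss distributions. This is an inexpensive improvement worth making before abstraction starts, not a flaw that invalidates the study.

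**What to change.** Keep switchers in the study and make these changes to the protocol and CRF:

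1. For Saxenda patients, add one CRF item recording any Victoza or other GLP-1 receptor agonist prescription in the 12 months before the first Saxenda prescription: brand, first and last date, last dose and indication.
2. State which weight counts as initial in the analysis of patients with prior liraglutide.
3. Do not count prior Victoza alone as evidence of dysglycaemia when its recorded indication was weight management.
4. Report the BMI/comorbidity, dose-escalation and stopping-rule endpoints overall and separately for patients with and without prior liraglutide.
5. Keep patients who started both brands after launch in the Saxenda group, and report Victoza use for weight management among them separately from the recorded indication. Reassigning them to the first brand started would take actual Saxenda users out of the primary objective and thin the very stratum to be reported.

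The cost is one more abstraction item from the same chart and additional table columns. At the assumed shares the switcher stratum would hold about 15–30 of the 150 full-study Saxenda patients, so its estimates would be imprecise and should be presented as such.

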Based on the data obtained in the pilot study, full study refinements may be necessary before the full retrospective medical record review is implemented in the two countries.

The index date, defined as the start date of data abstraction, will be 6 months after the launch of Saxenda[®] for the pilot, and 24 months after launch for the full study (see Figure 1 for an overview of the study design). The launch date may be different in the two countries. The data will be collected only after informed consent has been obtained from the patients. All study prescribers within a country will be assigned the same index date and will not be contacted prior to it. Initiation of prescriber-specific activities for selection of patient records meeting study selection criteria will commence on or following the index date. Data on drug utilisation will be censored on the index date. This approach will ensure that study procedures do not influence prescribing practices.

 Protocol
 Date:
 23 November 2015
 Novo Nordisk

 Study ID: NN8022-4241
 Version:
 5.0

 UTN: U1111-1185-3661
 Status:
 Final

Page:

20 of 53

CONFIDENTIAL

[figure not shown]

Figure 1 - DUS overview

EU PAS No .:

Notes: The index date (start date of data abstraction) for the pilot study will be 6 months following the launch of Saxenda[®] in the participating countries; data will be collected on patients from their start date of Saxenda[®]/Victoza[®] until the index date for the pilot study. The index date for the full study will be 24 months after the launch of Saxenda[®]; data will be collected on patients from their start date of Saxenda[®]/Victoza[®] until the index date for the full study. ICF: Informed Consent Form; M: month

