8.4 Data sources

Retrospective abstraction of data from patient medical records will be performed by trained healthcare professionals or external medical record abstractors. Data for each patient will be recorded in accordance with normal clinical practice and no additional assessments or tests considered as interventional will be required. Data obtained from the pilot study on physician (type of specialty), site (geographic location, practice type, size and patient volume) and patient (using retrospective abstraction of data from patient medical records) representativeness will be the basis for the feasibility assessment of the full DUS.

Concomitant medication with GLP-1 receptor agonists entered into the CRF will be coded using the WHO Drug Reference List.

Protocol		Date:	23 November 2015	Novo Nordisk
Study ID: NN8022-4241		Version:	5.0	
UTN: U1111-1185-3661		Status:	Final	
EU PAS No.:	CONFIDENTIAL	Page:	27 of 53	

All data will be entered pseudonymised into the CRF. See section 8.3 for the list of data to be collected; these data will be collected 6 months and 24 months after the launch of Saxenda[®], for the pilot and full study, respectively (see Figure 1).

The physician must keep a patient enrolment log and a log of patients evaluated for but not included in the study throughout the enrolment period. The log will include information on the number of patients approached to participate the study, the number of patients who accepted, the number of patients confirmed eligible, the number and reason patients were ineligible, and the number of patients who refused. These data will allow calculation of the participation rate. Each patient signing an informed consent form will be uniquely identified in the study by a patient identification number.

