8.7 Data analysis

All data analysis will be performed by

As this is a descriptive study that will investigate in-market utilisation of liraglutide, no formal statistical testing will be conducted.

Characteristics of study participants will be reported as mean, standard deviation, median, first and third quartiles and range for continuous variables and as number and proportion of patients with observed (non-missing) data for categorical variables. Study participation will be presented, including number of sites approached for the study and response rate, by specialty, and number of patients approached, response rates, and reasons for refusal. Characteristics of the participating sites and patients will be presented, stratified by country. The data may also be evaluated and presented for other meaningful subgroups of patients (e.g., by sex or age). Comparison between participants and non-participants will be made for sites and patients. Participating and non-participating sites will be compared on geographic location, area of primary practice, practice type, practice size and

Protocol		Date:	23 November 2015	Novo Nordisk
Study ID: NN8022-4241		Version:	5.0	
UTN: U1111-1185-3661		Status:	Final	
FILPAS No.	CONFIDENTIAL	Page.	29 of 53	

patient volume. Comparison of participating patients and the total population of patients treated with Saxenda[®] or Victoza[®] will be made, subject to data availability.

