8.9 Limitations of the research methods

As this is a non-interventional study, potential bias cannot be ruled out.

Data collection will reflect routine clinical practice rather than mandatory ass

Data collection will reflect routine clinical practice rather than mandatory assessments at prespecified time points, which may have an impact on the amount of data available and its interpretation.

Biases

Selection bias

 Protocol
 Date:
 23 November 2015
 Novo Nordisk

 Study ID: NN8022-4241
 Version:
 5.0

 UTN: U1111-1185-3661
 Status:
 Final

Page:

35 of 53

In order to minimize selection bias, the sampling strategy that was designed for the proposed study, will truly reflect real-life clinical practice since it will capture all possible treatment settings. In addition, selection bias due to sampling and participation will be addressed by comparing selected characteristics of the study patients and prescribers with those recorded in an external national database (IMSLifeLink).

Information bias

EU PAS No .:

At the prescriber (site) level, information bias is mitigated by the retrospective design. This study involves no intervention and treatment of patients considered eligible and their medical records at a site have been completed prior to the country-specific index date. Thus, the knowledge about this study (and its conduct) will not have had impact on the standard medical care and Saxenda® or Victoza® prescription practices at a site and will not have affected the treatment of patients. Data collected from medical records will therefore reflect real world medical practice.

At the patient level, misclassification of drug exposure has to be considered. Medical records provide detailed information on prescribed and/or dispensed medications but may not contain information on the intended duration of use (days of supply) and often do not contain information on the actual use of the medications by the patient. Thus, patients may be classified as exposed to a drug although they actually have not taken the drug. For this reason, great care will be taken to ensure the quality of the information that is abstracted, and prescribers' follow-up by clinical research associates (CRAs) will be enforced.

Missing Data

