9.1 Informed consent form for study patients

Informed consent from all study participants is required.

In obtaining and documenting informed consent, the physician must comply with the applicable regulatory requirement(s) and adhere to the requirements in the Declaration of Helsinki (8).

Prior to any study-related activity, the physician must give the patient both oral and written information about the study in a form that the patient can read and understand. This includes the use of impartial witness where required.

A voluntary, signed and personally dated, informed consent form will be obtained from the patient prior to any study-related activity. Consent can be obtained both onsite during a visit or remotely. In

Protocol		Date:	23 November 2015	Novo Nordisk
Study ID: NN8022-4241		Version:	5.0	
UTN: U1111-1185-3661		Status:	Final	
EU PAS No.:	CONFIDENTIAL	Page:	37 of 53	

that latter, the physician will send two copies of the Informed Consent Form (ICF) to the patient's house who will sign both, keep one and send back the other in a pre-stamped envelope to the physician.

The task of seeking informed consent can only be performed by the physician or another medically qualified person delegated by the physician, if permitted by local regulation, who must sign and date the patient information/informed consent form. If information becomes available that may be relevant to the patient's willingness to continue participating in the study, the physician must inform the patient in a timely manner and a revised written informed consent must be obtained.

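### Consent is sought only after the index date, so patients still on treatment may be easier to enrol; this would bias the duration endpoint, and the site log as listed would not show it

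*Protocol*

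**What the plan says.** Consent comes first and contact comes late. Protocol 8.2.2 requires "Informed consent obtained before any study-related activities", and 8.1.1 adds: "The data will be collected only after informed consent has been obtained from the patients". The same section says of timing: "All study prescribers within a country will be assigned the same index date and will not be contacted prior to it". The index date is 6 months after launch for the pilot "and 24 months after launch for the full study", and drug-use data are censored there.

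On how consent is obtained, 9.1 states: "Consent can be obtained both onsite during a visit or remotely". The remote route is postal, with a pre-stamped return envelope. It is allowed, not required.

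On participation, 8.4 provides a log: "The log will include information on the number of patients approached to participate the study". It also counts those who accepted, were eligible, were ineligible (with reason) or refused. Section 8.7 promises: "Comparison between participants and non-participants will be made for sites and patients". It adds a comparison with all treated patients if data are available. Section 8.9 names selection through sampling and participation, refers it to a comparison with an external prescription database, and says that the sampling strategy "will truly reflect real-life clinical practice since it will capture all possible treatment settings". Section 8.2.5 gives a similar assurance of generalisability.

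**The concern.** Every patient is asked for consent after the treatment period under study has ended. Whether the patient was still on treatment at that point is itself an outcome: section 7.3 counts patients as ongoing or by duration class, and the stopping-rule endpoints count patients who continue treatment.

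A patient who still receives prescriptions comes to the site and can be asked there. One who stopped many months earlier may have no visit. Sections 8.2 and 8.2.5 describe how prescribers are sampled. No section calls for a random, consecutive or complete approach to patients within a site, and the target of 75 per brand per country (8.2.1) could be filled from patients who attend.

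If enrolment depends on treatment status, the duration results describe those who persisted more than those who started. The retrospective design guards against prescribers changing their behaviour, but not against this, because the selection happens after follow-up closes.

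**Working it through.** The plan gives no figure for this bias, so there is none to reproduce. The enrolment ratio below is an assumption.

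**Timing.** Section 5 has pilot data collection starting in November 2016. If that is 6 months after launch, launch was about May 2016 (the two countries may differ). Full-study collection runs from April 2018 to February 2019. The latest consent could then fall about 33 months after the earliest treatment starts.

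**Duration endpoint.** Let p be the true share ongoing at the index date, and r the probability of enrolment if ongoing divided by that if stopped. Then

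- observed ongoing share = rp / (rp + 1 − p)
- each completed-duration class is multiplied by 1 / (rp + 1 − p), if all stopped patients are equally likely to be enrolled.

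With p = 30% (assumed):

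| r | Observed ongoing | Multiplier for each stopped class |
|---|---|---|
| 1 | 30% | 1.00 |
| 1.5 | 0.45/1.15 = 39% | 0.87 |
| 2 | 0.60/1.30 = 46% | 0.77 |
| 3 | 0.90/1.60 = 56% | 0.63 |

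The full study has 2 × 75 = 150 Saxenda patients. The 95% half-width at 30% is 1.96 × √(0.3 × 0.7/150) = 7.3 points. The shift at r = 1.5 is already about 9 points.

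A simulation with uniform initiation over 24 months and a median persistence of 9 months (both assumed) points the same way. As r goes from 1 to 2 to 3, the ongoing share goes from 46% to 63% to 72%, and the share stopped within 6 months from 33% to 23% to 17%. Medians of 6 and 12 months give the same direction.

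**Stopping-rule endpoint.** Continuing at 16-24 weeks is not the same as being on treatment at the index date. Suppose 60 of the 150 patients lose less than 5% and 20 of them continue (33%). Suppose also that 30% of those 20, that is 6, are still ongoing at the index date. The 40 who stopped are off treatment, so

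- among patients with less than 5% loss: (6r + 14)/(6r + 54) = 20/60 = 33% at r = 1, 26/66 = 39% at r = 2, 32/72 = 44% at r = 3
- among all 150, with 45 (30%) ongoing: (6r + 14)/(45r + 105) = 20/150, 26/195 and 32/240, each 13.3%.

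In a simulation with 35% losing less than 5% and half of them stopping, the true share among all patients is 17.4%. At r = 2 and 3 it becomes 18.7% and 19.3% if later discontinuation is equal in both groups (0.05 per month). It becomes 16.0% and 15.3% if patients with less than 5% loss stop faster later on (0.12 against 0.04 per month). With all patients as denominator the direction is not fixed.

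**Safeguards.** The items listed for the log in 8.4 include neither treatment status nor patients identified but not reached. If stopped patients are never approached, the participation rate can look high when the bias is largest. The external comparison in 8.1.1 and 8.9 and the total-population comparison in 8.7 name no measure of persistence.

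**The case against.** The strongest reply is that nothing in the protocol shows that patients on treatment will be over-represented. No consent rates by treatment status are given. The postal route in 9.1 reaches patients who no longer attend. Section 8.9 names participation bias and opens by conceding that bias cannot be ruled out. Section 8.1.1 uses the external database to assess patients as well as prescribers, 8.7 adds response rates and reasons for refusal, and the characteristics to be compared may be specified elsewhere. All of this stands. It makes the bias a risk rather than a fact, and it means that the comparisons may not reveal the problem, not that they cannot.

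A reader might also infer that non-adherence to the stopping rule must be overstated, and by a lot. Applying the ratio to all 20 who continued gives 20r/(20r + 40), that is 50% and 60% at ratios 2 and 3. That treats everyone who continued at 16-24 weeks as still on treatment at the index date. A patient who continued past week 24 and stopped at month 10 is off treatment when consent is sought. The documents support neither those figures nor a fixed direction, because 7.3 reports counts and 8.7.2 does not fix the denominator at patients with less than 5% loss.

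The scope is also limited. The BMI and comorbidity endpoints are fixed at initiation and do not measure continuation directly, the duration endpoint is secondary, and the gap is shorter in the pilot.

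**Conclusion.** The point holds as a risk that the design creates and the listed safeguards may not show. That consent follows the index date, that stopped patients need not be approached, and that the log lists neither treatment status nor unreached patients all follow from the text. That patients on treatment enrol more readily is likely but assumed; at a ratio of 1 there is no bias.

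If the ratio exceeds 1, the ongoing share is too high and early discontinuation too low. A true 30% would be seen as 46% or 56% at ratios of 2 or 3, more than sampling error explains. The stopping-rule proportion rises among patients with less than 5% loss (33% to about 39% or 44% under the assumptions above), but may rise, fall or stay the same among all patients. The assurances in 8.2.5 and 8.9 rest on the range of prescribers and settings, so they do not answer this. The change is cheap and worth making.

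**What to change.** 1. In 9.1, require the existing postal consent route for every identified eligible patient without a scheduled visit, whatever the current treatment status.
2. In 8.4, add aggregate counts to the site log, by brand and by on or off treatment at the index date, for patients identified, approached, unreachable, refusing and consenting. The protocol requires consent even before suitability is checked, so add these only as far as that requirement and local rules allow.
3. Report participation by treatment status, with a sensitivity analysis of the duration endpoint reweighted to the log's on/off distribution. The reweighted ongoing share is then simply the log's share; what is gained is rescaled stopped classes and a visible discrepancy. For the stopping rule, treat reweighting only as a sensitivity result, since status at the index date is not continuation at 16-24 weeks.
4. Qualify the representativeness statements in 8.2.5 and 8.9.

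The cost is some postage, extra log work and one more table, with a lower stated participation rate and slightly wider uncertainty after reweighting. The log change should be made before consent begins, because missing counts are hard to recover later.
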